Low-intensity versus high-intensity home-based treadmill training and walking attainment in young children with spastic diplegic cerebral palsy

NCT #: NCT02424526

Date: 7/29/2014

Study Protocol and Statistical Analysis Plan

Study Design

This is a prospective randomized controlled study which will include 24 pre-ambulatory children with CP under 3 years of age (i.e. up to the child's third birthday), GMFCS levels I and II.

Study Sites

All assessments and interventions will be conducted at the children's homes. In order to achieve a culturally and ethnically diverse sample, children will be enrolled at three sites in two US states. [name] will enroll children at the Seattle, WA site, [name] will enroll children at the Tacoma, WA site and [name] will enroll children at the Sacramento, CA site. Seattle, WA has a relatively high-income White (non-Hispanic descent) and Asian urban population; Tacoma, WA has a relatively lower-income White, Black and Hispanic urban population; Sacramento, CA has a relatively middle-income Hispanic, Black and Asian urban and rural population.²³ Conducting the study at these 3 sites will enable us to better generalize the results to a larger population.

Participants and Characteristics

24 pre-ambulatory children with CP under 3 years of age, GMFCS levels I and II, with bilateral impairment, who show signs of walking readiness will be recruited at the 3 different study sites. Eight children will be randomly assigned to a low-intensity or a high-intensity treadmill training group at each site.

Inclusion criteria will include

- Signs of walking readiness as demonstrated by the ability to sit for 30 seconds when placed and to take 5 to 7 steps when supported at the trunk or arms. These criteria were used in previous research to assure that the children had sufficient trunk control and bipedal control for the treadmill intervention.¹⁷ Children will be pre-ambulatory and will not engage in regular ambulation with an assistive device outside of physical therapy.
- Because young children often are not formally diagnosed with CP until 2 years of age, we will include children
 - who show bilateral symmetrical or asymmetrical impairment (i.e. diplegia and quadriplegia, but not hemiplegia)
 - who demonstrate upper motor neuron signs (i.e. spasticity and/or hyperreflexia)
 - who have been identified as high-risk for a motor disability by a physician

Exclusion criteria will be

- a history of uncontrolled seizures

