Due to their young age, some of the children, particularly those in the high-intensity group, might have difficulty maintaining attention to the task during the intensive intervention. In order to keep them motivated during the treadmill walk, the treadmill will be placed in front of a TV or laptop showing an age-appropriate movie chosen by their parents. This technique has proven to be helpful in previous studies and has the added benefit of preventing the children from looking downward.^{17,20} In one previous study, the average daily time walked on the treadmill was 28.2 ± 11.2 minutes for the twice daily walking periods by a similar group of children using the above described motivational techniques.¹⁷

Some children might be unable or unwilling to hold onto the handle bars of the treadmill. In this case, a second parent will be necessary to help the child maintain grip of the handle bars. If a second person is not available, the child's hand can be loosely strapped onto the handle bar for the duration of the walk.

Outcome Measures

Each child will be tested at pre-intervention, post-intervention, at 1-month and at 4-months following the intervention.

Valid and reliable outcome measures at the *Body Structures and Functions Level* of the International Classification of Functioning, Disability and Health (ICF) Model²⁸ will include the 1-minute Walk Test. Outcome measures at the *Activity Level* of the ICF model will include the Gross Motor Function Measure-66 (GMFM-66), Peabody Developmental Motor Scales-2 (PDMS-2), Functional Mobility Scale (FMS), the Timed 10-meter Walk Test and the StepWatch accelerometer. Outcome measures at the *Participation level* of the ICF Model will be the Pediatric Evaluation of Disability Inventory Mobility Scale (PEDI). Videotapes of assessments will be scored by an assessor blinded to group allocation for the GMFM and PDMS-2.

- 1-minute Walk Test: The child's walking distance will be measured in meters over 1 minute at their self-selected walking speed if the child is able to walk with an assistive device. The 1-minute Walk Test is a reliable test of walking endurance in young children with CP, when administered after a practice trial. Due to the young age and early ambulatory status of the children, the 1-minute Walk Test is more appropriate than a 6- minute Walk Test.²⁹

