To assure sufficient power to assess the effects of treadmill training on overall walking activity, a proposed sample size of 12 per group would have 80% power to detect a 3000 stride/day difference in treatment intensity as measured with the StepWatch monitor. This is based on [name] cross-sectional StepWatch average stride/day data from 17 youth with CP ages 2-3 years where the mean difference between GMFCS level I and II was 3000 strides.¹⁸

[figure not shown]

Fig. 4. Power analysis for sample size ($\alpha = 0.0$; Power= 0.95; Effect size=1.87; Sample size=18)

Methodology

Approval from the University Institutional Review Board was submitted on July 10, 2014 and approved on July 29, 2014 by the lead institution at California State University, Sacramento. A cooperative agreement will be put in place prior to study onset with the other institutions (please see attached). Due to the children's young age, written informed consent will be obtained from the parents. Parents will be asked to commit to a 6-week stretch uninterrupted by vacations or breaks. Study participation will be discussed and scheduled carefully with the families to allow for 6 weeks of uninterrupted intervention period. Due to the nature of the home-based administration of the intervention by parents and caregivers, high adherence to the study protocol is expected. Investigators will schedule weekly home visits and all assessments at a mutually agreed upon time that is convenient for the families.

After consenting to study participation, the parents for each child will fill out a parent questionnaire containing demographic and health information about their child. A physician form will also be signed prior to study onset to seek medical clearance for the child for the intervention. Group allocation will be determined by blinded drawing from a hat until each of the three study sites has reached a total of 4 children in each group. In the unlikely event that one site might have difficulty with subject recruitment, additional children will be enrolled at another study site.

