Each child will be tested at pre-intervention, post-intervention, at 1-month and at 4-months following the intervention. The testing will be scheduled at a mutually agreed-upon and convenient time with the family at their home. The children will undergo 6 weeks of treadmill training in their homes administered by a parent or primary caregiver who has been trained to safely provide the intervention. Weekly visits will be conducted by the researchers to adjust the treadmill speed and make any needed corrections to the parents' technique. The treadmill speed will be increased each week as tolerated by the child. The speed will not exceed 0.6 meter/second. In a previous study by [name] using a similar sample and treadmill protocol, the average starting speed was 0.1 meters/second and increased to an average of 0.25 meter/second over the duration of 6 weeks.¹⁷ Children assigned to the high-intensity group will walk on the treadmill 5 days/week, twice daily for 10-20 min for 6 weeks. Children in the low-intensity group will walk on the treadmill 2 days/week, once daily for 10-20 minutes for 6 weeks. The children will be motivated during the treadmill walk with a child-friendly video shown on a television, computer, or tablet. If uninterested, children will be encouraged with other motivational toys suggested by the parents. These motivational methods led to high adherence in [name] previous study on a similar sample of young children with CP.¹⁷

There is a possibility that a child might miss a training session due to sickness or other family obligations. The parents will be encouraged to make up a missed session on a different day. In the low-intensity group, the children have 5 days/week without treadmill training that could be used as make-up days. In the high-intensity group, the children have 2 days/week without treadmill training that could be used as make-up days. If a missed day cannot be made up, the parents will be encouraged to attempt to

train for the maximal 20 minutes for each treadmill walk in order to make up some of the missed minutes during other walks. The parents will document the minutes walked and the speed of each treadmill walk on a paper flow chart that is provided to them by the PIs.

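### The 80% StepWatch power is for a gap between GMFCS levels, not a dose effect, so it does not assure an answer on training intensity and walking activity

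*Combined protocol and SAP*

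**What the plan says.** The Power Analysis section contains two calculations. The first uses PDMS-2 Locomotion change scores from an earlier home treadmill study. It gives 18 children, to which 6 are added to reach 24.

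The second concerns StepWatch. It opens with its purpose, "To assure sufficient power to assess the effects of treadmill training on overall walking activity", and says that 12 per group "would have 80% power to detect a 3000 stride/day difference in treatment intensity as measured with the StepWatch monitor". The stated basis is "cross-sectional StepWatch average stride/day data from 17 youth with CP ages 2-3 years", in which "the mean difference between GMFCS level I and II was 3000 strides". The section gives no SD, standardised effect, test or sidedness for this calculation. The parameters in the Fig. 4 caption (power 0.95, effect size 1.87, sample size 18) belong to the PDMS-2 calculation.

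Three other places bear on the point:

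- Participants and Characteristics admits children at both GMFCS level I and level II and randomises them between the two intensities.
- The last paragraph of Methodology makes overall walking activity part of specific aim 2 and says that between-group StepWatch differences will show it.
- Data Analysis sets alpha at 0.05 and assigns StepWatch a Wilcoxon signed rank test for paired data.

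**The concern.** A power statement says how likely the trial is to detect a given difference between its randomised arms. Here the difference was measured between children of two severity levels at one point in time. The source comparison involved no training contrast and no change within a child. Both severity levels can fall in either arm, so the 3000 strides/day describes a baseline characteristic and not the randomised contrast. The PDMS-2 calculation in the same section does start from change scores under treadmill training.

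What can be concluded from a null result is at stake. If the true dose effect is well below one GMFCS level, the trial would usually miss it. A protocol that says power was assured leaves a non-significant StepWatch result open to being read as evidence that intensity does not matter for walking activity.

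**Working it through.** **Inputs from the documents.** Target difference 3000 strides/day, 12 per group, power 80% (Power Analysis); alpha 0.05 (Data Analysis).

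**Assumptions.** Two-sided, two-sample t-test with equal SDs. The SD is not given.

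**Step 1: the plan's own figure.** The 80% cannot be reproduced without an SD, but it can be inverted. With n = 12 per group, the degrees of freedom are 2 × 12 − 2 = 22 and the critical value is 2.074. The noncentrality is d × √(n/2) = d × √6, where d is the difference divided by the SD. Power reaches 80% at d = 1.197 (noncentrality 2.93). The implied SD is 3000 / 1.197 = about 2,507 strides/day. The same method applied to the PDMS-2 calculation (d = 1.87, two-sided 0.05, 95% power) returns the plan's 9 per group, with 96.1% power. That supports the method but does not confirm the StepWatch SD.

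**Step 2: power for smaller differences at the implied SD.**

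| True difference (strides/day) | d = difference / 2,507 | Power at 12 per group | n per group for 80% |
|---|---|---|---|
| 3000 | 1.20 | 80% | 12 |
| 2500 | 1.00 | 65% | 17 |
| 2000 | 0.80 | 46% | 26 |
| 1500 | 0.60 | 29% | 45 |
| 1000 | 0.40 | 15% | 100 |

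The smaller differences are illustrative, because the documents give no dose effect on strides/day. If the true effect were half the GMFCS gap, the trial would miss it 100 − 29 = 71% of the time.

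**Step 3: sensitivity to the unstated test.** The effect needed for 80% power, and the SD it implies, are:

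- normal approximation, two-sided: d = 1.14, SD 2,623
- one-sided t-test: d = 1.05, SD 2,863
- two-sided rank test at 0.955 efficiency: d = 1.23, SD 2,444

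For a true difference of 1500, a one-sided t-test has 41% power if the SD stays at 2,507. At its own implied SD of 2,863 (d = 1500 / 2,863 = 0.52), it has 34%. Under each of these tests, 80% power needs an effect above 1 SD.

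**Step 4: sensitivity to the unstated SD.** With the two-sided t-test, power for the 3000 itself is 94% at SD 2000, 80% at 2500, 65% at 3000 and 52% at 3500. These SDs are an assumed range.

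**Step 5: precision.** At the implied SD, the 95% CI for the difference in means has a half-width of about 2.074 × 2,507 × √(2/12) = 2,120 strides/day. An estimate near zero would still be compatible with differences of about 2,000 in either direction.

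**Step 6: powered contrast against planned test.** The Power Analysis and Methodology sections both describe a difference between arms. A signed rank test on paired data addresses change within children, so it neither tests nor estimates that difference.

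**The case against.** The plan's sentence is conditional: it gives power to detect 3000 strides/day and does not say that 3000 is expected. One functional level can be defended as a benchmark for a worthwhile difference. StepWatch is one of seven measures, and the total of 24 comes from the PDMS-2 calculation, so the StepWatch figure does not set the sample size. Nowhere does the plan say that a null result will be read as no dose effect. The power table rests on a back-calculated SD and an assumed test.

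Most of this stands, and it limits the point. It does not remove it. The documents never argue for the benchmark, and the opening clause still claims assurance for the effect of training in general. The table is illustrative, but step 3 shows that the need for a very large effect does not depend on the choice of test.

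A reader might infer three stronger things that the documents do not support:

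- **That the 80% is wrong.** Without an SD this cannot be shown.
- **That 3000 is implausible because it exceeds the strides a child could take in a day's treadmill sessions.** StepWatch is worn before training starts and at the post-intervention assessments, so it captures everyday walking. Treadmill strides are no ceiling on that, and converting minutes and speed to strides needs a stride length that the documents do not give.
- **That recruiting pre-ambulatory children makes 3000 unreachable.** Children who start with little walking could change a great deal if they begin to walk, and their SD could be larger or smaller than in the source sample.

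**Conclusion.** The concern holds as a fault in how the target is justified and how the power claim is worded. The target is a cross-sectional gap between severity levels, presented as the difference to be detected between training intensities, with no argument that it is a dose effect or a minimum important difference. With a two-sided two-sample t-test at 0.05 and all 12 children per group analysed, the claim is true only for a difference of about 1.2 SD. If the SD is near the implied 2,500, a non-significant result would say little about differences of 2000 strides/day or less, where power is 46% or lower. The paired test in Data Analysis adds to the problem, because the plan as written would not produce the between-arm estimate that a reader needs to judge a null result. The figures for smaller differences depend on the assumed test and the back-calculated SD, and should be replaced by the sponsor's own.

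**What to change.** **Power Analysis.** Replace the opening clause of the StepWatch sentence, and claim 80% power only for a between-arm difference of about 1.2 SD (or the corresponding figure if the sponsor's test differs). Label 3000 strides/day as a GMFCS-level benchmark and not an expected dose effect. State the SD actually used, its source, the test and the sidedness. Give power at smaller differences, for example 2000, 1500 and 1000 strides/day, calculated from that SD. The back-calculated 2,507 should not be printed as the sponsor's figure.

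**Data Analysis.** Report StepWatch strides/day as a between-arm difference with its 95% CI. If a rank method is preferred, use a two-sample one with a matching interval. State that a non-significant result will not be read as absence of a dose effect and that the interval will be used to say which differences remain compatible with the data.

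Giving the SD or softening the wording alone would not be enough, because the planned paired test would still not estimate the powered contrast.

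**Cost.** A few sentences and a different StepWatch analysis on data already to be collected. No extra children are needed. The stated power will look less favourable.

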- a diagnosis of a genetic disorder
- cardiac or orthopedic contraindications for standing and walking
- orthopedic surgery in the past 6 months
- use of spasticity-reducing medication or Botox injections in the past 6 months
- participation in other previous or concurrent intensive physical therapy programs

Interventions

All children will continue their regularly scheduled physical therapy during the study period. Frequency of ongoing physical therapy interventions as well as the physical therapy approach will be recorded for each child. All interventions will be conducted at the children's homes. On the first visit, the

PI will provide a portable pediatric treadmill for the family's use at no charge for the duration of the intervention period. The treadmill is designed for research and is equipped with a non-resettable minute timer and adjustable handle bars.²⁷ There will be a one-week training period for each child to familiarize the family with the treadmill intervention. After initial set-up of the treadmill, the PIs will conduct weekly visits to the family. The children will undergo 6 weeks of treadmill training in their homes administered by a parent or primary caregiver who has been trained to safely provide the intervention. The weekly visits will be conducted by the PIs to adjust the treadmill speed and make any needed corrections to the parents'/caregiver's technique.

Children assigned to the high-intensity group will walk on the treadmill 5 days/week, twice daily for 10-20 min for 6 weeks. Children in the low-intensity group will walk on the treadmill 2 days/week, once daily for 10-20 minutes for 6 weeks. The parents will be encouraged to take a break on two days of their choice, depending on the family's other commitments. The treadmill speed will be determined based on previous protocols developed by [name].¹⁷ The initial treadmill speed will be set at the maximum speed at which the child can maintain walking without dragging his/her feet for more than 3 seconds. The treadmill speed will be increased during the weekly investigator visits as tolerated by the child, using the same criterion. The children will wear shoes and/or their customary orthotics during the walking. The treadmill speeds will not exceed 0.6 meters/second, which is the maximal speed available on the pediatric treadmills. It is anticipated that all children will walk at a speed between 0.1 and 0.3 meters/second.

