- StepWatch data will be collected for all awake daytime hours over a 7 day period at study onset before treadmill training commences and at each of the post-intervention assessments. The StepWatch accelerometer has been shown to reliably measure walking activity in children with CP.²⁶ To assure consistency in data collection, study investigators will participate in a 2-day training session prior to study onset. Training in use of StepWatch accelerometers and treadmills, standardization of training protocols and administration of outcome measures will assure inter-rater reliability.

Enrollment procedures

An equal number of children will be enrolled at each site for a total of 8 children per location. Of these eight children, four children will be randomly assigned to the low-intensity and four will be assigned to the high-intensity group. Randomization will be conducted via blinded drawing from administrative personnel at their respective sites.

The PI and C-PIs are all engaged in clinical practice at their facilities and have professional connections with medical and therapy facilities in their communities. At each site, advertisement for the study will be conducted via posted flyers, electronic flyers and word-of-mouth recruitment.

[name] will recruit children from Alta Regional Center Sacramento, the area's main provider of early intervention services, from Easter Seals Sacramento, from Shriners Hospital Northern California, from University of California Children's Hospital, from Sutter Hospital Sacramento, and via the Sacramento Pediatric Therapy Interest Group. [name] successfully recruited from these sources for past studies and is known for her research in the medical and therapy community. Staff support for recruitment will come from professional connections at each recruitment site and at the University.

[name] will use a directed recruitment mailing to children and their families who have received care at Seattle Children's Hospital and to community therapy providers in Western Washington State. Seattle Children's Hospital provides care to ~ 800 children with cerebral palsy each year primarily through Developmental and Rehabilitation medicine departments. [name] has an extensive history of recruitment for clinical trial for children with CP (i.e. Selective Dorsal Rhizotomy, Botox and Intrathecal Baclofen).

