[name] will recruit from local early intervention providers (including Birth to Three Developmental Services, A Step Ahead in Pierce County, and Tacoma Learning Center), Mary Bridge Children's Hospital, the Children's Therapy Unit, and from Washington Pediatric Special Interest Group. [name] has successfully recruited subjects from these sites previously.

No problems with recruitment of study participants are anticipated due to each investigator's connections in their local medical community. If one of the sites should fall short of qualified children, more children could be covered at one of the other sites. Drop-out rates are expected to be low due to the home-based nature of the study. All of the outcome measures as well as the intervention will be conducted at the children's homes. It is possible that a young child might fall sick for any of the planned visits by the PIs, or might not fully participate in one of the visits for other reasons. In this event, the PI will reschedule a repeat visit within a few days of the original visit to collect the data.

Between the three sites, twelve children will receive high-intensity treadmill training and twelve children will receive low-intensity treadmill training. Due to the stringent inclusion and exclusion criteria, the children in the two groups are expected to show no significant between-group differences at baseline. In [name] previous study on home-based treadmill training, group allocation using the same criteria led to two groups with no significant differences regarding age and developmental skills.¹⁷

Power Analysis

Power analysis was conducted to determine a sample size based on developmental data and based on StepWatch data.

To examine the optimal dosing for walking attainment, a projected sample size of 18 subjects (9 per group) at 95% power was calculated from Peabody Developmental Motor Scales-2 Locomotion subscale change scores from [name] previous home-based treadmill training study (n=12; GMFCS levels I and II; ages 15-32 months)¹⁷. An additional 6 subjects will be added to strengthen the study design and allow for possible attrition, leading to a total number of 24 subjects.

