The study protocol was submitted to the Institutional Review Board (IRB) at California State University, Sacramento, on July 10, 2014 and approved on July 29, 2014 (IRB protocol #13-14-156). In addition, the consent form, permission to be videotaped, parent questionnaire and physician form for the study were all approved by the IRB. Once the grant is received, a cooperative agreement form will be signed by the two participating universities before the study commences.

Selection of the families will be made by judgment of the PI. Factors will include parental ability to correctly perform the treadmill training and safety during treadmill training sessions. The PIs reserve the right to terminate participation in the study if parents are unable to adhere to the agreed-upon treatment regimen, or display incorrect or unsafe technique during training. Any adverse events will be reported to the IRB. Because this intervention is conventionally used in physical therapy practice, adverse events are not anticipated. A small incentive will be offered to families to encourage participation. The families have the right to terminate participation in the study without any reason or penalty.

The study will be conducted in the children's homes. The last names of the children will not be used when other persons are present in the area. The PIs will abide by Health Insurance Portability and Accountability Act (HIPAA) regulations on children's privacy. When reporting results, only ages, diagnosis, functional level and gender of children will be reported. Photographs and/or video clips of children might be used when reporting results, but only with written permission of the parents/guardians. No mention of exact geographical location will be made.

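### Drawing to exactly 4:4 at each site makes about 60-67% of allocations guessable (chance is 50%) to PIs who also select the families, and leaves extra children without a draw rule

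*Combined protocol and SAP*

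**What the plan says.** **Allocation.** Enrollment procedures plans eight children per site: "Of these eight children, four children will be randomly assigned to the low-intensity and four will be assigned to the high-intensity group". The same section gives the totals: "Between the three sites, twelve children will receive high-intensity treadmill training and twelve children will receive low-intensity treadmill training". It also says who draws: "Randomization will be conducted via blinded drawing from administrative personnel at their respective sites". Methodology adds that the method is "blinded drawing from a hat until each of the three study sites has reached a total of 4 children in each group", and describes this after consent, the parent questionnaire and the physician form.

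**Selection and contact.** Human Subjects states "Selection of the families will be made by judgment of the PI" and lists the parent's ability to carry out the training among the factors. Under Interventions, "the PIs will conduct weekly visits to the family", and the visits serve to adjust speed and correct technique. The arms differ in days per week and in sessions per day. The only blinding described, apart from the draw itself, is of the video assessor for the GMFM and PDMS-2.

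**Entry and overflow.** The Overall Study Timeline gives each site two treadmills for its eight children. If a site falls short, "more children could be covered at one of the other sites"; Methodology repeats this allowance. Neither section says how those extra children are drawn.

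**The concern.** A block of fixed, known size can be partly read from its own history. Once a site has had, say, three high-intensity and one low-intensity allocation, the next child is more likely to be low-intensity, and anyone who knows the counts knows that. Having administrative staff draw the lot hides the current lot but not what remains.

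This matters because the people who very likely know the counts also decide which families enter. Part of that decision concerns how well a parent will deliver a parent-administered intervention, which is plausibly related to outcome. A PI with a sense of the next arm could, without intending to, bring forward a more able child or a more committed family. Adjusting for baseline motor scores would not fully remove such a difference, because no baseline measure of parent commitment is listed. Blinded video scoring guards against biased assessment, not biased entry.

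**Working it through.** **1. The plan's own totals.** 3 sites x (4 + 4) = 24, and 3 x 4 = 12 per arm. This matches Enrollment procedures. The documents give no figure for predictability.

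**2. Guessing rule.** The PI guesses the arm with more places left at the site, and guesses at random when the two are equal. A 4:4 block has C(8,4) = 70 equally likely sequences.

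**3. One child at a time, lots drawn without replacement.** With m = 4 per arm, expected correct guesses = m + 2^(2m-1)/C(2m,m) - 1/2 = 4 + 128/70 - 0.5 = 5.33 of 8 (67%). Enumerating all 70 sequences gives the same. By position, the chance of a correct guess is 50, 57, 57, 63, 63, 71, 71 and 100%. On average 1.6 of 8 allocations are certain beforehand.

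**4. Other readings of the procedure.** The documents do not say what the hat holds or whether families are chosen singly, so two variants are shown.

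| Reading | Correct of 8 | Share | Certain of 8 |
|---|---|---|---|
| One at a time, without replacement | 5.33 | 67% | 1.6 |
| Fair draw until one arm has 4 | 5.09 | 64% | 2.2 |
| In pairs, both families chosen before either draw | 4.83 | 60% | 0.9 |
| Chance | 4.00 | 50% | 0 |

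The paired row uses the same 70 sequences, with counts updated only after every second child. By pair, the chance of a correct guess is 50, 57, 63 and 71%, so 2 x (0.500 + 0.571 + 0.629 + 0.714) = 4.83.

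**5. Possible bias (assumption, not in the documents).** Suppose the PI's choice moves a child's prognosis by +s SD when one arm is guessed and by -s SD when the other is, always favouring the same arm. Then bias = 2 x s x (2 x correct - 8)/8.

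- One at a time: s = 0.25 gives 2 x 0.25 x 2.66/8 = 0.17 SD; s = 0.5 gives 0.33 SD.
- In pairs: s = 0.25 gives 2 x 0.25 x 1.66/8 = 0.10 SD; s = 0.5 gives 0.21 SD.

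For entry one at a time, a simulated two-sided 5% t test on 24 children then rejects a true null about 6.5% of the time (s = 0.25) to 10% (s = 0.5). The t test is a simple stand-in, not the planned analysis.

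**6. One central 12:12 list.** A PI who sees only own-site allocations guesses 4.26 of 8 (53%, by simulation). A PI who sees all 24 as they occur guesses 14.6 of 24 (61%). The number in one arm among a site's eight children is hypergeometric (24, 12, 8): P(3 to 5) = 0.81 and P(2 to 6) = 0.97.

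**The case against.** Much of the case for the plan stands. Staff other than the PI make the draw, and it is described after consent and medical clearance, so the current lot is concealed. Stratifying by site is reasonable when the sites were chosen to differ in income and ethnicity. Two treadmills per site suggest that children may enter in pairs, which lowers the guessable share to 60%. The bias figure needs a consistent preference for one arm and a surplus of eligible families. The documents show neither; they call the criteria stringent and plan for a shortfall. The assumed s of 0.25-0.5 SD also means a contrast of 0.5-1.0 SD between children chosen for one guessed arm and for the other, which is large.

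Four stronger readings are tempting, and the documents do not support them:

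- A reader might infer that the PI can foresee two thirds of allocations. Two thirds is the upper figure for correct guesses, of which half would come by chance; only 0.9-2.2 of 8 (11-27%) are known in advance.
- A reader might infer that the last child at each site is always certain. That fails if children enter in pairs or a site takes extra children.
- A reader might infer that the hat runs out of lots for extra children. Its contents are not described; what is missing is a rule.
- A reader might infer that parent commitment goes wholly unmeasured. Parents log minutes and speed, and the treadmill has a timer, but these records arise after allocation and cannot serve as baseline adjustment.

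None of this removes the core point: the remaining composition at a site can be read from its past allocations, and no section requires the decision on a family to be fixed before the next arm can be inferred.

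**Conclusion.** The concern holds as a modest, conditional risk. Under the 4:4 rule, a PI who knows earlier allocations can guess 60-67% of them correctly, an excess over chance of 0.83 to 1.33 children per site of eight. That the PIs know earlier allocations is inferred from the weekly visits and the visible difference between arms; the plan does not say so. The bias of 0.10-0.33 SD is an illustration that depends on the assumed shift, a constant direction and a choice among families. It is not an estimate for this trial, and nothing shows that selection was or would be distorted.

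Separately, and without any assumption about behaviour, the stopping rule of four per arm at every site and the allowance for extra children at another site do not fit together, because no draw rule covers those children. The change is worth making because it is cheap and cannot be made after enrolment.

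**What to change.** Replace the site hats with one concealed, computer-generated 12:12 list for all 24 children, held by the statistician at the lead institution. Release each assignment only after consent, physician clearance, the PI's written accept/decline decision on the family and the baseline tests are on record. Extra children at any site take the next place on the list, which closes the overflow gap.

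Do not share running counts with any investigator. Human Subjects has the PI handling all data entry, so arm labels should be kept out of what that PI enters while enrolment is open. The gain depends on this: the guessable share is 53% if PIs see only their own site's allocations, but about 61% if one sees them all.

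Add site as a factor in the repeated-measures ANOVA; Data Analysis has no such factor now. The Friedman and Wilcoxon analyses (PEDI, FMS, StepWatch) cannot take it.

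**Cost.** One list, revised wording in Enrollment procedures, Methodology and Data Analysis, and no extra staff. Site splits may drift from 4:4: they stay at 3:5 or closer with 81% probability and at 2:6 or closer with 97%. For the rank-based outcomes that drift would not be adjusted for.

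**If exact 4:4 per site must stay,** record the accept/decline decision for every family approached, in order and before the draw. This does not make allocations harder to guess, but it lets a reader check whether selection followed them. A written draw rule for extra children is then still needed.
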